#### **7.1.4. Weeks 2, 8, and 16 [ ± 1 day]**

Study staff at Stanford will call the subject on the phone and query subject and/or caregiver regarding any changes in general health and the use of concomitant medications. We will review previous and current concomitant medications. We will instruct the subject and/or caregiver of the excluded medications and answer any question that the subject may have.

#### **7.1.5. Weeks 4 and 12 [ ± 14 days before or after scheduled visit] at subject's cooperating research site or at Stanford if the subject is local to Stanford.**

1. If the subject is being seen at a cooperating research site the subject will need to review the purpose and nature of the study with the local investigator at the cooperating site. If not already done before local laboratory tests, eye and hearing exams prior to the screening visit at Stanford, the subject's parent or legally authorized representative must read, sign, and date the IRB-approved informed consent document for the local cooperating research site. The subject's assent to participate in the study will be obtained if the subject is between 7 and 10 years of age. The informed consent document must be signed and dated by the individual who consents the subject. A photocopy of the signed informed consent document will be provided to the parent or legally authorized representative. A copy of the informed consent will also be placed in the subject's medical record. A copy will be sent the Stanford. The original copy will be maintained in the research files. This consent will document the cooperation of the Stanford site and the local cooperating research site.

2. Query subject and/or caregiver regarding any changes in general health and the use of concomitant medications. Obtain demographic information and review interim medical history, including information on all medications currently being taken. Review previous concomitant medications and current concomitant medications. Instruct the subject and/or caregiver of the excluded medications and give them a list if they do not have their list with them.
3. If any adverse events are observed or reported, they must be recorded as instructed in Section 13, Adverse Events.
4. Review criteria for treatment discontinuation. If treatment must be permanently discontinued, proceed to Section 7.1.12 for Early Exit.
5. Perform a physical examination including heart and pulmonary auscultation, liver and spleen palpation, abdominal auscultation and palpation, and documentation of peripheral pulses. Examine and describe the characteristics of their lymphatic malformation.
6. Obtain Vital Signs including height, weight, temperature, heart rate, blood pressure, respiratory rate, and oxygen saturation.
7. Clinical assessment of each lymphatic malformation including measuring the hemicircumference of the lesion by using a soft measuring tape placed on the skin over the area of the widest diameter of the lesion. The length, and width, will then be calculated as describe in Figure 2 of Berk et al (2011). In order to document the site of the measurements a diagram will be drawn by hand or photographs will be taken of the methods. Each clinic visit will try to duplicate the measurements methods used in the initial visit.
8. Completion of subject's evaluation of the change in lesion clinical characteristics from baseline, such as decreased discomfort, texture or thickness, distortion of normal anatomy or overall change obtained in the subject's completion of *Subject's Assessment of Lymphatic Malformation Change* form.
9. Completion of the physician's evaluation of the lesion clinical characteristics on the day of the visit. This includes color, tenseness and texture, superficial component, deep component, and distortion of anatomical landmarks. This requires completion of the *Lymphatic Malformation Assessment* form for each LM site.
10. Physician's evaluation of the change in lesion clinical characteristics from baseline, such as change in texture or thickness, change in distortion of normal anatomy, and over change in lesions. This requires completion of the *Lymphatic Malformation Assessment of Change* form for each LM site.
11. Count study drug and perform compliance assessment; medication journal reviewed.

12. Study medication dose will be calculated based upon the weight of the subject during the visit. The Stanford site will be notified of the weight and dose. The Stanford physician will notify the pharmacy of the subject number and proposed dose. The Stanford pharmacy will dispense adequate study medication (sildenafil or placebo) to last until the next visit. The medication will be shipped directly to the subject's home.
13. Review possible adverse events included in informed consent.
14. New medication journals reviewed and instructions reviewed.
15. Arrange a MRI examination to be done before the 20 week visit at Stanford.
16. Instruction sheet will be given to the subjects documenting contact information for the research physicians and excluded medications and foods while on sildenafil if they do not have the instruction sheet previously given to them.
17. If a subject approves, the Stanford site or the local cooperating research site will send a copy of the dictated record for the study visit to their local primary care doctor and/or pediatric dermatologist and other specialty physicians that the subject requests. If the subject is to be followed at one of the local cooperating research sites, a copy to the record will be sent to the Stanford site. We would like to be sure that the physicians in the subject's home community are aware of the study and the subject's participation in the study.

#### **7.1.6. Week 20 [ ± 21 days before or after scheduled visit] at Stanford**

End of Treatment for subjects treated with sildenafil. Possible commencement of treatment for those subjects on placebo.

1. Query subject and/or caregiver regarding any changes in general health and the use of concomitant medications. Obtain demographic information and review interim medical history, including information on all medications currently being taken. Review previous concomitant medications and current concomitant medications. Instruct the subject and/or caregiver of the excluded medications and give them a list if they do not have their list with them.
2. If any adverse events are observed or reported, they must be recorded as instructed in Section 13, Adverse Events.
3. Ophthalmology evaluation, hearing exam, and blood draw performed. Subjects from cooperating research study sites will have the option to do these tests at their local site or at Stanford.
4. Perform a physical examination including heart and pulmonary auscultation, liver and spleen palpation, abdominal auscultation and palpation, and documentation of

peripheral pulses. Examine and describe the characteristics of their lymphatic malformation.

5. Obtain Vital Signs including height, weight, temperature, heart rate, blood pressure, respiratory rate, oxygen saturation.
6. Clinical assessment of each lymphatic malformation including measuring the hemicircumference of the lesion by using a soft measuring tape placed on the skin over the area of the widest diameter of the lesion. The length, and width, will then be calculated as describe in Figure 2 of Berk et al (2011). In order to document the site of the measurements a diagram will be drawn by hand or photographs will be taken of the methods. Each clinic visit will try to duplicate the measurements methods used in the initial visit.
7. Photographs of the Lymphatic malformation will be taken using standardized procedures described in Baseline Visit.
8. Completion of subject's evaluation of the change in lesion clinical characteristics from baseline, such as decreased discomfort, texture or thickness, distortion of normal anatomy or overall change obtained in the subject's completion of *Subject's Assessment of Lymphatic Malformation Change* form.
9. Completion of the physician's evaluation of the lesion clinical characteristics on the day of the visit. This includes color, tenseness and texture, superficial component, deep component, and distortion of anatomical landmarks. This requires completion of the *Lymphatic Malformation Assessment* form for each LM site.
10. Physician's evaluation of the change in lesion clinical characteristics from baseline, such as change in texture or thickness, change in distortion of normal anatomy, and over change in lesions. This requires completion of the *Lymphatic Malformation Assessment of Change* form for each LM site.
11. Collect study drug and perform compliance assessment; medication journal reviewed.
12. Obtain a pregnancy test if the subject is has achieved menarche.
13. The participant or parent/guardian and the investigator will complete the qualitative assessment of efficacy. The subject's evaluation of the response to the treatment will be reviewed. The results report of the MRI done at the twenty week visit will be shared with the subject and compared with the initial MRI reported results. After that discussion the subject will be told if they were on sildenafil or placebo. Subjects who received placebo will be given the option to start the sildenafil. Subjects who received active medication will be requested to stop the sildenafil for the next twelve weeks and follow up at the 32 week visit to examine the response of the lesion off of the sildenafil.

14. If subject received placebo and decides to receive sildenafil at this time, the study medication dose will be calculated and obtained from the pharmacy for adequate study medication to last until the next visit in 4 weeks. The 2 hour monitoring will be completed after the first dose as described in Baseline visit. For more detail, see Section 7.1.7. If the subject was on placebo and elects not to start sildenafil they will not need to return for the 32 week evaluation.
15. If the subject received placebo and decides to not receive sildenafil they will end the study at this time and complete additional information needed for the End of study 32 week visit described in 7.1.7. below.
16. If a subject approves, we will send a copy of the dictated record for the study visit to their local primary care doctor and /or pediatric dermatologist so that the physicians in their home community are aware of the study and the subject's participation in the study.

**7.1.7. End of Study 32 weeks [ $\pm$  2 Weeks] at subject's cooperating research site or at Stanford if the subject is local to Stanford for subjects who are on active sildenafil for the initial twenty weeks of the trial**

1. Query subject and/or caregiver regarding any changes in general health and the use of concomitant medications. Obtain demographic information and review interim medical history, including information on all medications currently being taken. Review previous concomitant medications and current concomitant medications. Instruct the subject and/or caregiver of the excluded medications and give them a list if they do not have their list with them.
2. If any adverse events are observed or reported, they must be recorded as instructed in Section 13, Adverse Events.
3. Perform a physical examination including heart and pulmonary auscultation, liver and spleen palpation, abdominal auscultation and palpation, and documentation of peripheral pulses. Examine and describe the characteristics of their lymphatic malformation.
4. Obtain Vital Signs including height, weight, temperature, heart rate, blood pressure, respiratory rate, and oxygen saturation.
5. Clinical assessment of each lymphatic malformation including measuring the hemicircumference of the lesion by using a soft measuring tape placed on the skin over the area of the widest diameter of the lesion. The length, and width, will then be calculated as describe in Figure 2 of Berk et al (2011). In order to document the site of the measurements a diagram will be drawn by hand or photographs will be taken of the methods. Each clinic visit will try to duplicate the measurements methods used in the initial visit.

6. Completion of subject's evaluation of the change in lesion clinical characteristics from baseline, such as decreased discomfort, texture or thickness, distortion of normal anatomy or overall change obtained in the subject's completion of *Subject's Assessment of Lymphatic Malformation Change* form.
7. Completion of the physician's evaluation of the lesion clinical characteristics on the day of the visit. This includes color, tenseness and texture, superficial component, deep component, and distortion of anatomical landmarks. This requires completion of the *Lymphatic Malformation Assessment* form for each LM site.
8. Physician's evaluation of the change in lesion clinical characteristics from baseline, such as change in texture or thickness, change in distortion of normal anatomy, and over change in lesions. This requires completion of the *Lymphatic Malformation Assessment of Change* form for each LM site.
9. If a subject approves, we will send a copy of the dictated record for the study visit to their local primary care doctor and/or pediatric dermatologist and other specialty physicians that the subject requests. If the subject is to be followed at one of the local site cooperating research site, a copy to the record will be sent to Stanford. We would like to be sure that the physicians in their home community are aware of the study and the subject's participation in the study. By this visit the results of the segmentation analysis should be in the subjects Medical Record as an Addendum. Besides sharing this information with the subject, the information will be available for the subject's physicians.
- 10 After this visit the Stanford site will request the subject's parent or guardian's consent for a separate Stanford IRB-approved long term follow up protocol. If the subject is between 7 and 10 years old, we will request their assent. We will contact the subject on the phone if they are not at the Stanford site for the 32 week visit.

**7.1.8. Baseline Active [Day 0 (medication dispensed)] at Stanford for subjects who are on placebo for the initial twenty weeks of the trial**

For those subjects who were on placebo and request that they begin sildenafil, the first dose of the medication will be dispensed in the clinic, as described in the original baseline visit, Section 7.1.3. This visit will follow the same procedures described in Section 7.1.3.

**7.1.9. Weeks 2 Active, 8 Active, and 16 Active [ ± 1 day]**

These phone calls will follow the same procedures described in Section 7.1.4.

**7.1.10. Weeks 4 Active and 12 Active [ ± 14 days before or after scheduled visit] at subject's cooperating research site for subjects who are on placebo for the initial twenty weeks of the trial**

These visits will follow the same procedures described in Section 7.1.5.

**7.1.11. Week 20 Active [End of Treatment, ± 21 days before or after scheduled visit] at Stanford for subjects who are on placebo for the initial twenty weeks of the trial**  
This visit will follow the same procedures described in Section 7.1.6, except that there is no unblinding and no option to start a treatment period of active sildenafil.

**7.1.12. Week 32 Active [ End of Study, ± 2 Weeks] at subject's cooperating research site for subjects who are on placebo for the initial twenty weeks of the trial**  
This visit will follow the same procedures described in Section 7.1.7.

**7.1.13. Early Exit at subject's cooperating research site or at Stanford**

In addition to the procedures required at the EOT visit:

1. The subject will be exited from the study.
2. Study medication will be collected. The subject may elect to not return to Stanford or the cooperating research site for this visit. In this case, we will have them mail the unused medication back to Stanford. We will give them pre-addressed shipping forms. If the subject does not return for this visit, we may also arrange to get the pregnancy test at a local hospital or local office.

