  - Distance and angle of each photograph relative to subject will be documented at baseline and repeated for all subsequent photographs.
  - Photograph 1: front-on view of each lymphatic malformation.
  - Photograph 2: side-on view of each lymphatic malformation (to visualize thickness).
8. Review possible adverse events included in informed consent.
9. Medication journals will be given and instructions reviewed.
10. Study medication dose for 1 month will be calculated and obtained from the pharmacy. Subjects will receive an oral suspension of the study medication (see Section 18.2 for pharmacy instructions).
11. The first dose of the medication will be consumed in the clinic. The subject will remain within the clinic area and temperature, heart rate, blood pressure, respiratory rate, and oxygen saturation will be repeated every 30 minutes for the initial 2 hours after the initial dose.

12. Instruction sheet will be given to the subjects documenting contact information for the research physicians and the foods and medications to be avoided while on sildenafil.
13. If there are no safety issues identified during the 2 hours of observation, the participant or parent/guardian is dispensed enough study treatment until the next visit at Week 4 and the participant may leave the site. The subject and/or caregiver will again be instructed of the excluded medications and the list will again be reviewed. The subject will be advised to stop medication and notify the study team immediately if they notice a change in vision or hearing or if they feel dehydrated.
14. If a subject approves, we will send a copy of the dictated record for the study visit to their local primary care doctor and/or pediatric dermatologist and other specialty physicians that the subject requests. If the subject is to be followed at one of the local cooperating research sites, a copy to the record will be sent to the center. The MRI results, ophthalmology report, hearing test report and laboratory data will also be sent to the subject's local cooperating research site. We would like to be sure that the physicians in their home community are aware of the study and the subject's participation in the study.

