**7.2. DISCONTINUED SUBJECTS**

Discontinued subjects are those who voluntarily discontinue participation, who are withdrawn for safety reasons or use of prohibited concomitant treatments, or who have missed a sufficient number of study visits, procedures or test medication doses as to be ineligible for further participation.

All subjects who discontinue the study prior to completing the regularly scheduled visits must complete the EOT and Exit Visit procedures described in Section 7.1.11. Any changes in medical health and/or the use of concomitant treatments must be captured. If any adverse events were observed since the previous visit, they must be recorded

(refer to Section 13, Adverse Events). Finally, if appropriate, the Investigator also should advise the subject's parent or legally authorized representative of subsequent therapy and/or procedures necessary for their medical condition.

In the case of subjects who persistently fail to return for scheduled visits, three attempts must be made to contact the subject's parent or legally authorized representative for the purpose of scheduling an Exit/EOS Visit. The third attempt should be via registered mail, return receipt requested.

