### **10.3. SAFETY**

All subjects who receive study medication will be evaluable for the safety analysis. Summary statistics will be provided with respect to patients requiring discontinuation from treatment and from study (any reason and for safety reasons). AE summaries will focus on treatment-emergent AE and will summarize subject AE incidences by severity, seriousness, and relationship to treatment. Vital signs, laboratory tests, and concomitant medication usage will be displayed as listings by subject.

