## 16. STUDY PLAN

Table 16-1: Study Procedures by Treatment Day

| Visit:  | Screening
(Day -7 to +1) | Baseline &
Baseline-A 
(Day 0) | Week 2 &
Week 2-A 
(~4 1 Day) | Week 4  &
Week 4-A 
(~4 14 Days) | Week 8 &
Week 8-A 
(~4 1 Day) | Week 12  &
Week 12-A 
(~4 14 Days) | Week 16 &
Week 16-A 
(~4 1 Day) | Week 20 &
Week 20-A 
(~4 14 Days) | End of Study 
Early Exit 
(Week 32)
(~4 14 Days) |
|---|-----------------------------|--|---|--|---|--|---|---|---|
| Procedures:                            |                             |  |   |  |   |  |   |   |   |
| Informed Consent/Accent                       | x                           |  |   |  |   |  |   |   |   |
| Inclusion/Exclusion criteria                  | x                           |  |   |  |   |  |   |   |   |
| Vital signs (height, weight, HR, BP, temp)    | x                           | x  |   | x  |   | x  |   | x   | x   |
| Complete history                              | x                           |  |   |  |   |  |   |   |   |
| Interval history                              |                             | x  | x   | x  | x   | x  | x   | x   | x   |
| Physical examination                          | x                           | x  |   | x  |   | x  |   | x   | x   |
| Phone call                                    |                             |  | x   |  | x   |  | x   |   |   |
| Assessment of LM by MD                        | x                           | x  |   | x  |   | x  |   | x   | x   |
| Assessment of LM by participant               |                             |  |   | x  |   | x  |   | x   | x   |
| LM measurements                               | x                           | x  |   | x  |   | x  |   | x   | x   |
| LM photographs                                | x                           | x  |   | x  |   | x  |   | x   | x   |
| Laboratory tests                              | x               |  |   |  |   |  |   | x   |   |
| Urine pregnancy test                          | x               |  |   |  |   |  |   | x                                       |   |
| Ophthalmology exam                            | x               |  |   |  |   |  |   | x                                       |   |

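### The protocol gives conflicting early-exit procedures: 7.1.13 and 7.2 bring in the eye, hearing and blood tests, while the Early Exit column of Table 16-1 leaves them blank

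*Combined protocol and SAP*

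**What the plan says.** Four places in the protocol bear on what happens when a subject leaves early.

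- Section 7.1.13 (Early Exit) sets out its steps "In addition to the procedures required at the EOT visit". Item 2 has study drug collected and lets the family choose not to come back for the visit.
- Section 7.2 says that subjects who discontinue "must complete the EOT and Exit Visit procedures described in Section 7.1.11". Section 7.1.11 is the Week 20 Active visit and follows 7.1.6 apart from the unblinding and the offer of active drug.
- Section 7.1.5 item 4, for Weeks 4 and 12, says: "If treatment must be permanently discontinued, proceed to Section 7.1.12 for Early Exit". Section 7.1.12 is the Week 32 Active visit and follows 7.1.7.
- Table 16-1 has one combined column for End of Study (Week 32) and Early Exit. Footnote 5 says that early leavers have no final MRI and that a urine pregnancy test will be attempted.

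The end-of-treatment visit is Week 20, which 7.1.6 opens by describing as "End of Treatment for subjects treated with sildenafil". Its item 3 reads "Ophthalmology evaluation, hearing exam, and blood draw performed". At baseline (7.1.3 item 13) the subject is "advised to stop medication and notify the study team immediately if they notice a change in vision or hearing". On analysis, 10.3 states: "All subjects who receive study medication will be evaluable for the safety analysis"; 10.1 says the same.

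**The concern.** The eye, hearing and laboratory tests have two scheduled time points, Screening and Week 20. The one exception is that an unsuccessful screening hearing test is repeated at later visits. For a subject who leaves before Week 20, the exit visit is therefore the only scheduled occasion for a post-dose eye or laboratory result, and usually for a hearing result. Whether those tests are done depends on which part of the protocol the site follows.

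The protocol treats vision and hearing as matters to watch, since it names changes in them as reasons to stop the drug and contact the team. If early leavers are not tested, the Week 20 results could mainly describe children who stayed on treatment, and their number could be mistaken for the number dosed. A test not done at exit cannot be recovered later.

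**Working it through.** There is no planned figure to reproduce. The check traces each route to its end and reads the Early Exit column row by row.

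**Routes**

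1. 7.1.13 leads to the end-of-treatment visit, 7.1.6, whose item 3 has eye, hearing and blood tests.
2. 7.2 leads to 7.1.11, then 7.1.6 item 3, with the same three tests.
3. 7.1.5 item 4, read literally, leads to 7.1.12, then 7.1.7, which lists none of the three.
4. In Table 16-1 the row "Ophthalmology exam" is marked at Screening and Week 20 only. The laboratory and hearing rows are the same, so the combined column is blank for all three.

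**Side by side**

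| Item at early exit | 7.1.13 and 7.2 | Table 16-1, combined column | 7.1.5 item 4, literal |
|---|---|---|---|
| Eye examination | yes | blank | not listed |
| Hearing test | yes | blank | not listed |
| Blood tests | yes | blank | not listed |
| Drug collection | yes | blank | not listed |
| Pregnancy test, post-menarche | yes | blank; footnote 5 says attempted | not listed |
| MRI | part of Week 20 | blank; footnote 5 says none | not listed |
| Vital signs, physical examination, adverse events | yes | marked | listed |

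Of the three tests at issue, 7.1.13 and 7.2 include 3 of 3, the table 0 of 3, and the literal 7.1.5 route 0 of 3.

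**Does correcting the section numbers resolve it?** No. If 7.1.5 item 4 and 7.2 both pointed to 7.1.13, the table would still be blank for the three tests and for drug collection. The MRI would also still conflict, because the Week 20 procedures that 7.1.13 brings in include one and footnote 5 rules it out.

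**Upper bound on numbers.** Section 5.1 gives a goal of 40 subjects completing 20 weeks with an MRI and up to 60 enrolled. The Synopsis expects 55 to be enrolled and start medication.

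- 60 − 40 = 20, and 20/60 = 33%
- 55 − 40 = 15, and 15/55 = 27%

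This treats every subject in the gap as an early exit handled from the table. The documents state no dropout rate, so it is a worst case and not a forecast.

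**The case against.** The case for a milder view is substantial, and much of it stands.

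**The 7.1.5 pointer is a numbering slip.** This stands. Item 4 names Early Exit, and only 7.1.13 has that title. Similar slips occur elsewhere: adverse events are cited as Section 13 but are in Section 12, and the opening of Section 7 cites Table 17-1 for what is Table 16-1. The pointer is best not read as a second procedure list. The reference to 7.1.11 in 7.2 looks like the same kind of slip.

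**The table is only a summary, and visibly incomplete for early exits.** This is partly right. Its pregnancy-test cell is blank although footnote 5 promises an attempt. But Section 7 opens by sending staff to this table for the procedures required at each visit. Footnote 5 adapts the column to early leavers without mentioning the eye, hearing or blood tests, so a site could reasonably conclude that none is due.

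**Other provisions protect the subject.** Section 12.7 provides follow-up for adverse events unresolved at discontinuation, 7.1.14 allows unscheduled examinations at the investigator's discretion, and 6.1 remarks that local screening tests make re-testing easier. These are real but partial: none requires an eye, hearing or laboratory test.

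**Missing results would show.** Section 10.3 presents laboratory tests as listings by subject, where a gap can be seen, and summarises adverse events for all dosed subjects. That limits the risk of misreading. But 10.3 names no presentation of eye or hearing results and no count of subjects tested.

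A reader might also infer that early leavers provide no post-dose safety information at all. The documents do not support that: the combined column marks vital signs, physical examination and adverse event review, and vital signs are followed for two hours after the first dose.

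**Conclusion.** The inconsistency holds. Sections 7.1.13 and 7.2 on one side, and the Early Exit column of Table 16-1 with footnote 5 on the other, cannot both be followed. A site using the table would obtain no required post-dose eye, hearing or laboratory result from an early leaver, possibly including a child who stopped permanently after a change in vision or hearing.

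Two stronger readings should be resisted.

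- A reader might infer that children who stop for a vision or hearing change are exactly the ones left unexamined. Section 7.1.3 tells them to stop and report, not to exit. Early Exit follows only permanent discontinuation, and 6.1 and 12.7 anticipate some follow-up.
- A reader might infer that the trial expects to lose 27% to 33% of these results. The 40 is a goal and the 60 a ceiling. The gap could also include recruitment shortfall or completers without an MRI, and some early leavers may be handled under 7.1.13. The 15 to 20 subjects are an upper bound under the stated assumption, and the inconsistency does not depend on it.

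Any tilt of the safety results towards children who stayed on treatment is therefore possible but unquantified. This is an internal inconsistency rather than a design choice. It does not touch the primary analysis, has partial safeguards and is repaired by text edits. It should be corrected, but ranks below a must-fix.

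**What to change.** 1. Reconcile 7.1.5 item 4, 7.1.13 (including its option not to return), 7.2, Table 16-1 and footnote 5 into one early-exit list. Cover the eye, hearing and laboratory tests, drug collection, the pregnancy test and the MRI. Which of these an early leaver has is for the sponsor and clinicians to decide; this review takes no position.
2. Give Early Exit its own column in Table 16-1, separate from Week 32, matching the agreed list.
3. Correct the cross-references in 7.1.5 item 4 and 7.2 so that both point to the Early Exit section.
4. In 10.3, add a summary by arm of how many dosed subjects have a post-dose eye, hearing and laboratory result, so that a missing examination is not read as a normal one.

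The cost is a few text edits and one extra summary. Some families may still decline the exit visit, so reconciliation may reduce the missing results without removing them. The counts in step 4 are useful whichever list is adopted.
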